## 2.4 Study Endpoints

### 2.4.1 Primary Endpoint

The primary outcomes/endpoints are the changes from baseline (BSL), where baseline is the day before the infringement. Abbreviations for visits are defined in section 3.7.1.

- Delta from BSL to V2R (Day 42±3) = Mucus score at V2R - score at V2R-1 (Day 41±3): change from baseline to 3 (delayed pill period) or 6 hour (missed pill period) after infringement
- Delta from BSL to V2R+1 (Day 43±3) = Mucus score at V2R+1 - score at V2R-1 (Day 41±3): Change from baseline to just before pill intake the day after infringement
- Delta from BSL to V3R (Day 70±3) = Mucus score at V3R - score at V3R-1 (Day 69±3): Change from baseline to 3 (delayed pill period) or 6 hour (missed pill period) after infringement
- Delta from BSL to V3R+1 (Day 71±3) = Score at V3R+1 - score at V3R-1 (Day 69±3): Change from baseline to just before pill intake the day after infringement

The subordinate primary endpoint is the proportions of subjects with “protective effect of cervical mucus” the missed pill period and the delayed pill period for the following categories:

- Full protection by cervical mucus regardless of the use of norgestrel 75 mcg
- Absence of risk increase further to delayed intake
- Absence of risk increase further to missed pill
- Absence of risk increase due to infringement regardless of the type
- Transient risk increase further to delayed intake
- Transient risk increase further to missed pill
- Prolonged risk increase further to delayed intake
- Prolonged risk increase further to missed pill

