The **primary model** of interest is a mixed model for repeated measures using as response delta to  $V_{2R}$ , delta to  $V_{2R+1}$ , delta to  $V_{3R}$  and delta to  $V_{3R+1}$ . The covariates will be the period (or period effect), the intervention (type of infringement: missed pill or delayed pill), the sequence of intervention (missed pill then delayed pill and vice versa), the time (visit) and the subject. Time, period intervention type, and sequence will be considered as categorical variables. The subject as random effect (RANDOM statement of the MIXED procedure). This will permit to take into account the fact that measures from each period are derived from the same subjects. A time repeated effect (REPEATED statement of the MIXED procedure) within each combination subject\* period (SUBJECT = subject\* period as option of the

REPEATED statement). This will permit to take into account the fact that for each subject, at each period several measures are performed over time. The proper structure of the variance covariance matrix will be retained using the best fit among unstructured matrix (UN) compound symmetry (CS) and autoregressive structure (AR1).

The **primary test of interest** will be the significance of the overall mean (intercept). This will answer the question: is the overall mean change from baseline different from zero? Or does the infringement of schedule regardless the type of infringement lead to a change in mucus score?

The **contrasts or estimates of interest** are

- The effect of infringement type: does the effect of missed pill differ from the effect of 6 hours delay? If the answer is yes, then a signal of effect is detected.
- The effect of time: does the response on the day of infringement differ from the response on the day after infringement? If the answer is yes, then a signal of effect of infringement is detected.

The **primary cut-off** for full cervical mucus protection is a cervical mucus score of 4. There is, therefore, a good conception protection by cervical mucus if the cervical mucus score is  $\leq 4$ . If the cervical mucus was too thick to be collected (and thus a cervical mucus score could not be obtained) the analyses using the **FASM, ITT and PP populations** will use the following approach:

Baseline Mucus Score	Post-Baseline Mucus Score	Mucus Score Used in Analysis
0-4	Too thick to collect	Score equal to baseline
>4	Too thick to collect	Post-baseline score =4

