Too thick to collect	Any observed mucus score	Baseline score =0
Too thick to collect	Too thick to collect	Change from baseline = 0

A sensitivity analysis using the FASM population will also be done and if the cervical mucus was too thick to be collected (and thus a cervical mucus score could not be obtained) the mucus score will be assigned using multiple imputation.

The SAS code for the 2 primary contrasts of interest are:

```
PROC MIXED DATA=MUCUS;
CLASS VISIT PERIOD INTERVENTION SEQUENCE;
MODEL MUCUS_CHG = PERIOD INTERVENTION VISIT SEQUENCE / S;
RANDOM SUBJ_ID;
REPEATED / SUBJECT=SUBJ_ID*PERIOD;
ESTIMATE 'EFFECT OF INFRINGEMENT' INTERVENTION 1 -1 ;
ESTIMATE 'EFFECT OF TIME' VISIT 1 -1 1 -1;
RUN;
```

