Comparison between the missed pill and the delayed pill can easily be performed and tested through a stratified McNemar test (stratification on the site, CMH option in SAS). The SAS glimmix procedure for repeated measures was not retained for decision making test because convergence issues in fitting the model are too frequent. The first null hypothesis is  $H_0$ : Proportion of protected women at baseline (R-1) is equal to the proportion of protected women after schedule infringement and more specifically at Day R (27 hours and 30 hours post treatment). The second null hypothesis (which is only performed for the missed pill arm) is the equality of proportions at baseline (R-1) and at Day R+1 (48 hours post treatment).

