- (m) At V11, the mucus analysis will be performed before the 1st study medication intake
- (n) Mucus analysis to be performed at T2/3R-1 +8 h ± 30 min.
- (o) Mucus analysis to be performed at T2/3TR-1 +3h ± 15 min.
- (p) Mucus analysis to be performed at T2/3R-1 +6 h ± 15 min.
- (q) Mucus analysis to be performed within 30 min before study medication intake
- (r) Blood sampling for PK analysis at D1: subjects with even study number at predose, 2 h ± 15 min, 6 h ± 15 min and 12 h ± 30 min post-treatment and subjects with odd study number at 1 h ± 15 min, 4 h ± 15 min , 8 h ± 30 min and 24 h ± 30 min post-treatment

- (s) Blood sampling for steady state during first visit in week 3: subjects with odd numbers at predose, and between 0.5 h and 2h (morning visit), and subject with even numbers between 5 h and 9 h post-treatment (afternoon visit)
- (t) Blood sampling for compliance during 1st visit of weeks 5 and 9 within 30 min of cervical mucus sampling
- (u) Blood sampling for PK analysis at  $T2/3_{R-1} + 8h \pm 30 \text{ min}$
- (v) Blood sampling for PK analysis at  $T2/3_{R-1} + 3h \pm 15 \text{ min}$ ,  $T2/3_{R-1} + 5.5h \pm 15\text{min}$ ,  $T2/3_{R-1} + 7.5h \pm 30\text{min}$
- (w) Blood sampling for PK analysis at  $T2/3_{R-1} + 6h \pm 15\text{min}$
- (x) Blood sampling for PK analysis at  $T2/3_{R-1}$  within 30 min before study medication intake
- (y) No E2, FSH and LH measurements during extra-visits after postovulatory image is observed

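### Section 3.7.1 reads a pooled Day R versus Day R+1 difference as a sign of infringement effect, but that contrast has no perfect-use reference and averages over delayed and missed pill

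*SAP*

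**What the plan says.** SAP section 3.7.1 models changes from the R-1 baseline to Day R and Day R+1 in periods 2 and 3. The primary test is the overall mean change. Two further contrasts are named: infringement type and time.

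The time contrast asks "does the response on the day of infringement differ from the response on the day after infringement" and concludes "If the answer is yes, then a signal of effect of infringement is detected". No meaning is given to a negative answer. The code is "ESTIMATE 'EFFECT OF TIME' VISIT 1 -1 1 -1", in a main-effects model: "MODEL MUCUS_CHG = PERIOD INTERVENTION VISIT SEQUENCE / S". It has no intervention-by-visit term.

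The reading times are these:
- **Day R:** section 2.4.1 defines the endpoint as "change from baseline to 3 (delayed pill period) or 6 hour (missed pill period) after infringement". Under Subordinated Primary Objective the same readings are placed "at Day R (27 hours and 30 hours post treatment").
- **Day R+1, both types:** the footnotes to the Schedule of Assessments (5.1) say "Mucus analysis to be performed within 30 min before study medication intake". For the missed pill, the Subordinated Primary Objective compares proportions "at baseline (R-1) and at Day R+1 (48 hours post treatment").
- **Clock hours:** section 3.7.1 expects pill intake at about 9 am and takes the R-1 baseline about 8 h after intake.

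**The concern.** The study asks whether a delayed or missed pill changes the mucus score relative to perfect use on the day before. A comparison of two days that both follow the infringement answers a different question. Three things can go wrong when a difference is called an infringement signal:

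1. Delayed and missed pill may move in different directions between the two days, and pooling hides this.
2. The two days are read at different hours, so an ordinary difference between those hours would look the same as an infringement effect.
3. A rise of equal size on both days gives exactly zero.

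At stake is the reading of one of the two contrasts that the SAP introduces as primary. The study's main test is a separate matter.

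**Working it through.** The SAP gives no SD, power or expected value for this contrast. Section 2.5 says published data offer no basis for the variance, and its power figures concern proportions, so there is no plan figure to reproduce here.

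**1. The baseline cancels.** (score R − score R-1) − (score R+1 − score R-1) = score R − score R+1.

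**2. Both types get equal weight.** Each period holds one arm on delayed and one on missed pill. With equal arms, the coded contrast puts +0.5 on each of the four arm-by-period cells at Day R and −0.5 on each at Day R+1. With D for delayed and M for missed, this is (D_R − D_R+1) + (M_R − M_R+1).

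**3. Time since last pill** (T = usual intake time; late pill at T + 6 h, Schedule of Assessments):
- Delayed: Day R at 24 + 3 = 27 h, before the late pill. Day R+1 at (24 − 0.5) − 6 = 17.5 h after it.
- Missed: Day R at 24 + 6 = 30 h. Day R+1 at 48 − 0.5 = 47.5 h.

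The interval shortens in one type and lengthens in the other.

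**4. Clock hours.** With intake at 9 am, Day R is read near noon (delayed) or 3 pm (missed), Day R+1 near 8:30 am, and R-1 near 5 pm.

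**5. Illustrative rejection rates.** Assumptions: 45 women (completers, section 2.5), independent reading error with SD σ = 1.5 (range 1 to 2), two-sided 0.05, paired t-test with 44 df.
- Pooled: c = ½[(D_R − D_R+1) + (M_R − M_R+1)], variance ¼ × 4σ² = σ², SE = σ/√45. The factor ½ does not affect the test.
- Type-by-time: x = (D_R − D_R+1) − (M_R − M_R+1), variance 4σ², SE = 2σ/√45.

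At σ = 1.5 the SEs are 1.5/6.708 = 0.224 and 0.447. Examples:
- Delayed falls 1, missed rises 0.5: c = ½(1 − 0.5) = 0.25, noncentrality 0.25/0.224 = 1.12, 19%. For x = 1.5: 1.5/0.447 = 3.35, 91%.
- Clock difference of 0.5 only: |c| = 0.5, noncentrality 0.5/0.224 = 2.24, 59%. x = 0, 5%.

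| Change from R to R+1 | Pooled, σ = 1 / 1.5 / 2 | Type-by-time, σ = 1 / 1.5 / 2 |
|---|---|---|
| Delayed −1, missed +1 | 5 / 5 / 5% | 100 / 99 / 91% |
| Delayed −1, missed +0.5 | 37 / 19 / 13% | 100 / 91 / 69% |
| Delayed −0.5, missed +1.5 | 91 / 59 / 37% | 100 / 99 / 91% |
| Delayed 0, missed +1.5 | 100 / 91 / 69% | 100 / 91 / 69% |
| Equal sustained rise in both | 5 / 5 / 5% | 5 / 5 / 5% |
| Equal 1-point transient rise in both | 100 / 99 / 91% | 5 / 5 / 5% |
| No infringement effect, 0.5-point clock difference | 91 / 59 / 37% | 5 / 5 / 5% |
| 0.5-point shift at the missed-pill 6 h reading only | 37 / 19 / 13% | 37 / 19 / 13% |

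**6. Model size.** The coded fixed effects, with four-level VISIT absorbing PERIOD, have rank 6. A model with period, intervention, two-level visit, intervention-by-visit and sequence also has rank 6.

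**The case against.** Several points on the other side stand.

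- **Other planned tests cover much of this.** Suppose delayed is +1 then 0 and missed is +1 then +2. A test of the overall mean change, as section 3.7.1 describes it in words, would reject about 99.9% of the time at SD 1.5 (97% at SD 2). The type contrast would reject about 71% (48% at SD 2, 97% at SD 1). These figures also count the error in the baseline reading. The Subordinated Primary Objective defines transient and prolonged risk separately for each type and tests against R-1, although on the cut-off of 4 rather than on the score.
- **The 5% figure needs exactly equal and opposite courses.** A reader might infer that the contrast has almost no power in the expected pattern. The documents do not support that: they give the time since last pill, not the course of the score, and section 2.1 says no data link PK to PD. Under partial cancellation the rate at SD 1.5 runs from 19% to 59%, and it is 91% if only the missed pill moves.
- **A null is given no meaning.** A reader might infer that a null would be reported as no effect. Section 3.7.1 states only what a yes means.
- **No daily course is documented.** A reader might infer that false signals are to be expected. The SAP supports only the weaker statement that the contrast could not tell such a course from an infringement effect. Changes from R-1 share this weakness, because R-1 is read at yet another hour.
- **The type-by-time contrast is no full substitute.** It has no perfect-use reference either, and it misses an equal transient rise in both types (5%, against 99% for the pooled contrast at SD 1.5).
- **The study is exploratory.** That lowers the stakes, but it does not make the stated reading valid.

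**Conclusion.** The concern holds for the inference drawn from this one contrast. A pooled Day R versus Day R+1 difference cannot by itself be read as an infringement effect: the perfect-use reference has dropped out, two types with opposite changes in time since last pill are averaged, and the clock hours differ. It is also zero for an equal sustained rise.

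Those statements follow from the SAP's code and reading times alone. The rates (5% for exactly opposite 1-point courses, 19% for partial cancellation, 59% with a range of 37% to 91% for a 0.5-point clock difference alone) rest on an assumed SD, assumed effects and independent errors, and serve only as illustrations. The point does not reach the validity of the overall-mean test or of the type-specific proportions. It should be corrected before analysis, and the correction is cheap.

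**What to change.** In section 3.7.1 and its SAS code:

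1. Code VISIT with two levels (R, R+1) and add `INTERVENTION*VISIT` to the MODEL statement.
2. Add the type-by-time contrast, (delayed R − R+1) − (missed R − R+1), alongside the pooled time contrast and not in its place.
3. Report, separately for delayed and missed pill, the estimated change from R-1 at Day R and at Day R+1, and the R versus R+1 difference.
4. Keep the pooled time contrast as descriptive only, and delete the sentence that reads it as a signal of infringement effect.
5. State the limits. Neither time contrast has a perfect-use reference. The 3 h versus 6 h offset on Day R stays in the type-by-time contrast (a 0.5-point shift at the 6 h reading alone makes it reject about 19% of the time at SD 1.5). Changes from R-1 also compare different clock hours.

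**Cost:** a few lines of code and output, and no new data. The period-by-day term implied by four-level VISIT is dropped, and the intervention-by-day term takes its place, so the number of fixed-effect parameters is unchanged (rank 6 in both).

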### 2.3 Design

This is an exploratory, prospective, multi-center, randomized, cross-over study to assess the effect of norgestrel 75 mcg on cervical mucus and ovarian activity during reported perfect daily use and after a delayed intake of 6 hours and after a missed pill.

Women of reproductive age (18-35 years old inclusive) who meet eligibility requirements will be recruited for this study. This study has a screening period of up to 1 month to demonstrate ovulatory status prior to enrollment followed by three 28-day treatment periods (approximately 3 months) and a possible follow-up of 12 days if ovarian activity shows a follicle  $\geq 15$  mm is observed at the end of period 3 and an end of study (EOS) visit within 5 days. During the treatment period 2 the subjects will be randomized into two arms: Arm A will have a delayed pill intake of 6 hours on D42 ( $\pm 3$  days) and Arm B will have a missed pill (24-hour delayed pill intake on D42 ( $\pm 3$  days)). In the next treatment period, these subjects will cross-over meaning Arm A will have a missed pill (24-hour delayed pill intake) on D70 ( $\pm 3$  days) and Arm B will have a delayed pill intake of 6 hours on D70 ( $\pm 3$  days) (see Figure 1 below).

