## 2.5 Sample Size Consideration

Approximately 70 subjects will be screened to have at least 45 subjects who complete the study.

The primary analysis is based on the score of cervical mucus as a quantitative variable because it is expected to be the most powerful analysis based on the consistent mechanism of action of norgestrel on cervical mucus. However the justification of the sample size will not be based on the primary analysis as there is no basis provided by published data on this parameter, such as order of magnitude of the variance covariance matrix of the change from time point of reference. This is the reason why the sample size calculation will be based on proportions of women with no loss of protection.

A total sample size of 45 subjects who complete the study should allow to detect a loss of protection that would demonstrate a pertinent effect on a substantial proportion of the population. Indeed if the difference between a cycle (or day) with a perfect use and a cycle (or day) with an infringement in the schedule is 14 % in the expected proportions of women with a loss of protection at any time and if the proportion of discordances between the 2 situations is 17% then the exact power is equal to 79.1%. If the expected difference in proportions is 15% with a rate of discordance of 18% then the exact power is 82.4% for an unconditional test. The expected difference in proportions need, therefore, to reach 14-15 % to get a sufficient power for detecting a significant difference. This difference in proportions is a substantial difference knowing that most of change in status are in the same direction i.e. from protection to loss of protection.

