## 3.0 STATISTICAL METHODS

### 3.1 Statistical Handling Policy and Analysis Conventions

This section details general policies to be used for the statistical analyses. Departures from these general policies may be given in the specific detailed sections of this SAP. When this situation occurs, the rules set forth in the specific section take precedence over the general policies. The following policies will be applied to all data presentations and analyses.

- All statistical tests will use a significance level of  $\alpha = 0.05$ . Two-tailed tests will be performed for all analyses that use statistical testing.
- All p-values will be rounded to 3 decimal places. All p-values that round to 0.000 will be presented as '<0.001' and p-values that round to 1.000 will be presented as '>0.999'. Any

p-value  $\leq 0.05$  will be considered statistically significant and will be marked with one asterisk (e.g., 0.025\*).

- Summary statistics will consist of the number and percentage of responses in each category for discrete variables, and the mean, median, standard deviation (SD), minimum, and maximum for continuous variables.
- All mean values will be formatted to one more decimal place than the measured value. Standard deviation values will be formatted to two more decimal places than the measured value. Median values will be formatted to same decimal place as the measured values when that is possible without losing accuracy; otherwise, they will be formatted to one more decimal place than the measured values.
- All percentages will be rounded to one decimal place. The number and percentage of responses will be presented in the form XX (XX.X), where the percentage is in the parentheses. The denominator for percentage calculations will be the number of non-missing observations.
- All listings will be sorted for presentation in order of site number, subject number, and date of procedure or event.
- All analysis and summary tables will have the population sample size (n and % (% will not be shown in the column header if the table also presents means)) for each treatment group in the column heading.
- Calculating change from baseline to a visit will be done as follows: Change = Visit – Baseline.
- Baseline is defined as the last data point before the day of infringement (i.e. V2R-1 or V3R-1).
- Version 9.4 of SAS® or higher will be the statistical software package used to produce all summaries, listings, statistical analyses, and graphs.

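### Section 3.7.1 names one primary test, but also lets either of two ungated contrasts declare an effect and calls them primary; if all three count, the false-positive chance is about 14%

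*SAP*

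**What the plan says.** SAP section 3.7.1 fits a repeated-measures mixed model to four changes from baseline per woman: the day of infringement (R) and the day after (R+1), in each of periods 2 and 3.

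- **Named primary test.** It "will be the significance of the overall mean (intercept"), meaning whether the mean change differs from zero whatever the type of infringement.
- **Type contrast.** Under a separate label for contrasts or estimates of interest, the SAP treats a yes to the following question as finding a signal: "does the effect of missed pill differ from the effect of 6 hours delay? If the answer is yes, then a signal of effect is".
- **Time contrast.** This compares the response on day R with that on day R+1: "If the answer is yes, then a signal of effect of infringement is detected".
- **Code.** It is introduced with "The SAS code for the 2 primary contrasts of interest are". It holds one ESTIMATE statement for infringement type and one for time, and none for the overall mean.
- **Error level.** Section 3.1: "All statistical tests will use a significance level of" 0.05, two-tailed, for each test.

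The efficacy summary table in section 2.4.2 lists only a repeated measures mixed model against the four changes and does not say which model effect decides. Section 2.3 describes the design: "This is an exploratory, prospective, multi-center, randomized, cross-over study".

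**The concern.** The primary question is whether a delayed or missed pill changes the mucus score. Section 3.7.1 names one test to answer it, but two more tests carry sentences that turn a significant result into a detected effect. The SAP does not say what is concluded if the overall mean is not significant and one contrast is. Read literally, an effect of infringement is still declared.

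The labels also conflict within section 3.7.1. The text has one primary test, whereas the lead-in to the code has two primary contrasts, neither of which is that test. The named primary test is not programmed by an ESTIMATE statement. It is left to the intercept that the solution option prints, which in SAS's reference-cell coding is the mean for one combination of factor levels and not the overall mean.

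At stake is how the primary result will be read. Either contrast can be significant with no average change in score, while the working hypothesis in section 3.7.1 is a harmful one, an increase in score. The 5% in section 3.1 describes each test, not a conclusion that any of the three can trigger.

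**Working it through.** **Inputs.** Two-sided 0.05 per test (section 3.1). Three tests: overall mean, type, time (section 3.7.1). Sample: "A total sample size of 45 subjects who complete the study" (section 2.5). Layout: 2 periods × 2 visits. The SAP states no familywise error rate, so the only figure to reproduce is the 5% per test.

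**Step 1: are the three tests related?** Take the changes in the order period 2 R, period 2 R+1, period 3 R, period 3 R+1. For Arm A (delayed, then missed) the weights are:

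| Estimate | Weights |
|---|---|
| Overall mean | ¼, ¼, ¼, ¼ |
| Type (missed − delayed) | −½, −½, ½, ½ |
| Time (R − R+1) | ½, −½, ½, −½ |

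Arm B reverses the signs of the type row. The cross-products are:

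- mean × type: ¼(−½ − ½ + ½ + ½) = 0
- mean × time: ¼(½ − ½ + ½ − ½) = 0
- type × time: −¼ + ¼ + ¼ − ¼ = 0

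With a random subject effect, a baseline shared within period and equal residual variances, the three estimates are therefore uncorrelated. A generalised least squares calculation with 23 and 22 women per sequence also gave correlations of 0.

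**Step 2: error rates when all three nulls are true.**

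- Overall mean alone: 5%
- Either contrast: 1 − 0.95² = 9.75%
- Any of the three: 1 − 0.95³ = 1 − 0.857375 = 14.26%
- Upper bound under any dependence: 3 × 0.05 = 15%
- A contrast significant when the overall mean is not: 0.95 × 9.75% = 9.26% (equally, 14.26% − 5%)

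The remaining 0.05 × 9.75% = 0.49 points of the contrasts' error occur when the overall mean is also significant. So about 9.3 points, not the full 9.75, are added to the error of the primary test.

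**Step 3: simulation of the crossover** (45 women, 15,000 runs for each of three variance settings).

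| Quantity | Range over settings |
|---|---|
| Overall mean alone | 4.8% to 5.2% |
| Either contrast | 9.3% to 9.9% |
| Any of the three | 14.0% to 14.6% |

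A separate run of 40,000 gave 14.3% for any of the three and 9.3% for a contrast-only rejection.

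**Step 4: sensitivity.**

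- If the intercept is taken literally as the reference-cell intercept, it correlates with the contrasts at about −0.2 to −0.5, and the chance of any rejection is 13.4% to 14.0%.
- Positive equal correlations among the three would give 13.7% (0.3), 12.5% (0.5) or 10.9% (0.7). The balanced design gives no reason to expect them, and they are shown only as a range.

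**Step 5: effect of a rule.**

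- If only the overall mean decides, the error for that conclusion is 5%.
- If the contrasts are tested only after a significant overall mean, the chance of any false claim when all three nulls hold is also 5%, because no claim is possible without the first rejection.

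**The case against.** The strongest reply is that the SAP already has a hierarchy. It names one primary test, in the singular, ties it to the study question, and lists the two contrasts under a separate label. The sentences about a signal belong only to the contrasts, not to the overall mean. They can be read as interpretation: if missed and delayed pills differ, or if day R differs from day R+1, at least one mean change cannot be zero. The study is exploratory, signal is exploratory language, and no familywise error rate is promised.

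Much of this stands. A reader might infer that the primary test itself runs at 14%, or that the plan breaks a stated 5% familywise limit. The documents support neither. The named test keeps 5%, section 3.1 sets alpha per test, and an exploratory study need not control the error across all three. The 14% holds only if all three results count towards one conclusion.

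The reply does not remove the ambiguity. The logic of the signal sentences is sound for true means, but a significant p-value is not a true difference. The sentences say that an effect is detected and do not say that this is supportive of, or conditional on, the primary test. The code's lead-in then promotes both contrasts to primary. Calling the study exploratory does not settle which result answers the primary question.

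**Conclusion.** The point holds as an unclear and internally inconsistent decision rule for the primary analysis. The overall-mean test is sound at 5%. If a significant contrast also counts as showing an effect of infringement, as section 3.7.1 allows, the chance of at least one false positive is about 14%, of which about 9 points come from a contrast when the overall mean is not significant.

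These figures assume that all three nulls are true, that sequences are near balance with 45 completers, and that variances are equal. Reading the intercept literally lowers the total only to 13.4% to 14.0%. The change is worth making before analysis because it is cheap and follows the SAP's own choice of primary test. It does not call the design or the model into question.

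**What to change.** In SAP section 3.7.1:

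1. State that the conclusion on the primary hypothesis rests only on the overall mean change from baseline, tested at two-sided 0.05.
2. Add an ESTIMATE statement for that mean to the code, with coefficients written out so that it averages over the levels of period, intervention, visit and sequence.
3. Report the type and time contrasts as supportive estimates with 95% confidence intervals. Alternatively, test them only if the overall mean is significant; the documents give no reason to prefer one order. If they are tested side by side after the gate and the overall mean truly differs from zero, the pair still has a joint error of up to about 1 − 0.95² = 9.75%. That is acceptable for supportive results if it is stated.
4. Qualify the two sentences about a detected signal accordingly, and change the lead-in to the code so that it calls the contrasts supportive.

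**Cost.** SAP wording and one line of code. No data, visit or sample-size change, and both contrasts are still reported. The downside is that a contrast that is significant when the overall mean is not will be described, not declared a detected effect. In an exploratory study its estimate and interval remain visible to the reader.
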